## 10.6 Clinical Chemistries

Blood will be collected in serum separation Vacutainer™ tubes and serum separated according to standard procedures. Quantitative analysis will be performed for the following analytes: glucose, blood urea nitrogen, creatinine, total protein, albumin, bilirubin, alkaline phosphatase, AST, ALT, calcium, sodium, potassium, chloride, and carbon dioxide. The laboratory performing these assessments will be either directly regulated by CAP or CLIA or indirectly according to CLIA guidelines. The laboratory will need to provide a copy of the current certification. Blood chemistries will be performed at screening, intake, on Day 6, and at discharge.

## **10.7 Hematology**

Blood will be collected with appropriate anticoagulant and tested for complete blood cell count (CBC) with differential (absolute and percent) and platelets. The laboratory performing these assessments will be either directly regulated by CAP or CLIA or indirectly according to CLIA guidelines. The laboratory will need to provide a copy of the current certification. Hematology will be performed during screening, intake, on Day 6, and at discharge.

## **10.8 Urinalysis**

A dipstick urinalysis test will be performed during screening, intake, on Day 6, and at discharge.

## **10.9 Pregnancy Test**

A serum pregnancy test designed to measure  $\beta$ -HCG will be performed during screening and at intake. A urine pregnancy test will be done prior to cocaine infusion sessions 2-5 and at discharge.

## **10.10 Infectious Disease Serology**

Blood will be collected for HBsAg, HCVab, and HIV serology at Screening. These data will not be collected in the study database.

## **10.11 Cocaine Use by Timeline Follow Back Method**

Detailed histories of cocaine use over the past 30 days prior to screening will be obtained using the timeline followback method. In addition, the route of self-administration will also be collected. Participants must report administration by the i.v., nasal, or smoked routes to be eligible for the study. The timeline followback method was described and validated by Sobell *et al.*, (1986) for reporting alcohol use. It has also been found to be a reliable method for assessing the history of psychoactive substance use in drug-abusing populations (Fals-Stewart *et al.*, 2000).

## **10.12 Columbia-Suicide Severity Rating Scale (C-SSRS)**

The C-SSRS is a measure of suicidal ideation and behavior. At Screening, the “Screening/Baseline” version will be administered; on Days -3 and 11, the “Since Last Visit” version will be administered.

## **10.13 Beck Depression Inventory (BDI)**

This scale is a self-report measure of depression consisting of 21 items. The scale was developed to measure the behavioral manifestations of depression.

## **10.14 Beck Anxiety Inventory (BAI)**

This scale is a self-report measure of anxiety consisting of 21 items.

### **10.15 Concomitant Medications**

Concomitant medications will be assessed once a day by an investigative staff member. Any medications to be taken during the study must be approved by a site investigator/study physician.

### **10.16 Participant Disposition**

The Participant Disposition eCRF will be completed at the end of screening, treatment and follow-up that reports the status of the participant at each of these study periods.

### **10.17 Eligibility Checklist**

The Eligibility Checklist source document must be completed at the end of screening prior to make the decision for clinic intake and on the day of clinic intake prior to randomization and enrollment. This information will be used to determine whether the participant may be enrolled in the study. This form will document final eligibility and, if applicable, the reason the participant was not enrolled in the study. An inclusion/exclusion eCRF will be completed for screen failures to document the reason the participant was not eligible for the study.

### **10.18 Medical History**

A medical history will be taken on all potential study participants to assure medical fitness including questions about current and past opioid use, abuse, and dependence and recent smoking history. Women will be asked about their choice of method for birth control. Participants will be queried about recent alcohol and xanthine containing products consumption to assure eligibility.

### **10.19 MINI Neuropsychiatric Interview**

A MINI neuropsychiatric interview (version 7.0) (Sheehan *et al.*, 1998) will be administered during screening to rule out any major psychiatric disorders (*e.g.*, affective disorders, schizophrenia).

### **10.20 Physical Examination**

A physical exam of the oral cavity, head, eyes, ears nose and throat, cardiovascular system, lungs, abdomen (liver/spleen), extremities, skin, neuropsychiatric mental status and sensory/motor status, musculoskeletal system and general appearance will be performed during screening. Height and weight will be recorded during screening. A symptom directed physical exam will be performed at clinic intake and clinic discharge. Weight will be recorded at clinic intake.

### **10.21 Subjective Responses VAS**

The VAS is a self-administered assessment evaluating the subjective effects of cocaine. Participants will use an ePRO system provided by Technical Resources International, Inc., to

answer VAS. The participant should be instructed to respond to the questions with regards to how they feel at the moment of the assessment on a 100 mm Likert Scale with 0 being “Not at all” and 100 being “Extremely”. For the VAS, participants will report the degree to which they feel “any effects”, “high”, “good effects”, “bad effects”, “desire for cocaine”, “depressed”, “anxious”, “over- stimulated”, and “cocaine liking.”

VAS will be administered 30 minutes prior to cocaine infusion and at 5, 10, 15, 30, 45, 55, 65, 70, 75, 90, 105, 115, 125, 130, 135, 150, 165 and 180 minutes after the first infusion for screening infusion 1, and at -30, 5, 10, 15, 30, 45, 55, 65, 70, 75, 90, 105 and 120 minutes after the first infusion for baseline and treatment infusion Sessions 2 to 5. Windows for collection of VAS are nominal times  $\pm$  3 minutes for the first 30 minutes after the infusion and  $\pm$  5 minutes at all other time points.

## 10.22 Vital Signs

Vital signs (HR and BP) will be measured at screening and daily during inpatient stay. Additional vital signs will be monitored on cocaine infusion days (see Section 10.5, Table 3, and Table 4). Vital signs are assessed in semi-supine position.

## 10.23 Clinic Discharge/Final Participant Disposition

The participant disposition CRF will document all data relevant to participant discharge from the clinic: reason for discharge (*i.e.*, completion of inpatient portion of the study, or early termination from the study) and date of discharge.

# 11 REGULATORY AND REPORTING REQUIREMENTS

## 11.1 Good Clinical Practice

This study will be conducted in accordance with the most current version of the International Council for Harmonisation (ICH) Guidance Document *E6 (R2): Good Clinical Practices: Consolidated Guideline*. An Operations Manual will be provided to all investigational sites as a study quality assurance tool.

## 11.2 Form FDA 1572

The Principal Investigator will sign a Statement of Investigator (Form FDA 1572) prior to initiating this study. The Form FDA 1572 will be updated as needed.

## 11.3 IRB Approval

Prior to initiating the study, the Principal Investigator will obtain written approval from the IRB of record to conduct the study. Should changes to the study protocol become necessary, protocol amendments will be submitted in writing to the local IRB by the site Principal Investigator for IRB approval prior to implementation. In addition, NIDA and the local IRB will approve all advertising materials used for participant recruitment and any educational materials given to the

participant. Progress reports will be submitted to the local IRB annually or at a frequency requested by the IRB. The Investigator will report to the IRB all changes in research activity and all unanticipated problems involving risks to human participants or others.

#### 11.4 Informed Consent

All candidates for the study will be given the current IRB-approved Informed Consent Form (ICF) to read. The principal investigator or other study investigator will explain all aspects of the study, including its risks and benefit, in lay language and answer all of the candidate's questions regarding the study, and will ensure that each candidate understands the study prior to obtaining the participant's signature. If the candidate desires to participate in the study, s/he will be asked to sign the ICF. A copy of the consent form will be given to the participant. No study procedure will be performed prior to signing the ICF. Candidates who refuse to participate or participants who withdraw from the study will be regarded without prejudice.

#### 11.5 Outside Monitoring

**Medical Monitor:** A medical monitor has been appointed for the study. The medical monitor will be available for making recommendations to the Investigator and the Sponsor on the severity of any SAEs, the relatedness to the study interventions, and for determining if the SAE should be reported to the FDA in a 7 or 15 day expedited report or an annual report. The medical monitor will also be responsible for tracking and assessing trends in the AEs reported. In the event that the medical monitor and Investigator do not concur on SAE evaluations, both opinions will be reported to the FDA.

**Clinical Monitors:** All Investigators will allow representatives of the Sponsor to periodically monitor, at mutually convenient times during and after the study, all CRFs and corresponding source documents for each participant. These monitoring visits provide the Sponsor with the opportunity to evaluate the progress of the study and to inform the Sponsor of potential problems. The monitors will assure that submitted data are accurate and in agreement with source documentation; verify that the investigational product is properly stored and accounted for, verify that participants' consent for study participation has been properly obtained and documented, confirm that research participants entered into the study meet inclusion and exclusion criteria, and assure that all essential documentation required by GCP guidelines are appropriately filed.

Monitors will conduct a study initiation visit prior to the start of the study. At this visit, they will assure that proper study-related documentation exists, assist in training Investigators and other site personnel in study procedures and GCP guidelines, confirm receipt of study supplies, and assure that acceptable facilities and staff are available to conduct the study.

Routine monitoring visits by NIDA's representatives will be scheduled at appropriate intervals but probably more frequently at the beginning of the study. At these visits, the monitors will

verify that study procedures are being conducted according to the protocol guidelines and will review AEs and SAEs and drug accountability. At the end of the study, they will advise on storage of study records and return of unused investigational products. All sites should anticipate visits by NIDA and the FDA.

## 11.6 Adverse Events Reporting

In accordance with FDA reporting requirements, all AEs occurring during the course of the clinical trial will be collected, documented, and reported by the Investigator or sub-Investigators according to the specific instructions detailed in this section of the protocol and in [APPENDIX B](#). The occurrence of AEs will be assessed starting when the participant receives the first dose of study drug, then daily during the inpatient portion of the study until clinic release, and at the final follow-up telephone contact.

An AE is defined as any reaction, side effect, or untoward event that occurs during the course of the clinical trial, whether or not the event is considered related to the investigational product or clinically significant. For this study, events reported by the participant, as well as clinically significant abnormal findings on physical examination, vital signs, ECG, or laboratory evaluation will be recorded on the AE CRF. A new illness, symptom, sign or clinically significant clinical laboratory abnormality or worsening of a pre-existing condition or abnormality is considered an AE. Stable chronic conditions, such as arthritis, which are present prior to clinical trial entry and do not worsen are not considered AEs.

All AEs, recorded during the inpatient portion of the study regardless of severity, will be followed by study Investigator until satisfactory resolution. AEs must be reported up to the date of final follow-up following hospital discharge. At the follow-up phone call, AEs will be recorded and followed; they will be followed to resolution only if they are serious, or if the study Investigator assesses them to be clinically significant.

## 11.7 Serious Adverse Events

Each adverse event or reaction will be classified by a study Investigator as being serious or non-serious. Based on the seriousness of the adverse event or reaction, appropriate reporting procedures will be followed. The Code of Federal Regulations Title 21 part 312.32 and ICH *Guideline for Industry: Clinical Safety Data Management: Definitions and Standards for Expedited Reporting* (ICH-E2A), as implemented by the U.S. Food and Drug Administration (March 1995), defines a serious adverse event (SAE) or serious adverse drug experience as any untoward medical occurrence at any dose that:

- results in death;
- is life-threatening; (*NOTE: The term "life-threatening" in the definition of "serious" refers to an event in which the participant was at risk of death at the time of the event; it does not refer to an event which hypothetically might have caused death if it were more severe.*)

- requires inpatient hospitalization or prolongation of existing hospitalization;
- results in persistent or significant disability/incapacity; or
- is a congenital anomaly/birth defect.

In addition, important medical events that may not result in death, be life-threatening, or require hospitalization may be considered a serious adverse drug reaction, when based on appropriate medical judgment that may jeopardize the participant and may require medical or surgical intervention to prevent one of the outcomes listed in the above definition.

An unexpected AE is one that is not described with respect to nature, severity, or frequency in the current product package insert.

Reporting of AEs and SAEs is described in [APPENDIX B](#). There can be serious consequences including, ultimately, criminal and/or civil penalties for sponsors who fail to comply with FDA regulations governing the reporting of SAEs. The Investigators in this study have the responsibility of promptly reporting all SAEs to the designated Medical Monitor at NIDA in order that the NIDA can comply with these regulations.

If a study participant withdraws from the study or if an investigator decides to discontinue the participant from the study because of an SAE, the participant must have appropriate follow-up medical monitoring including, if necessary, hospitalization. Monitoring will continue until the problem prompting hospitalization has resolved or stabilized with no further change expected or is discovered to be clearly unrelated to study medication or progresses to death.

## 12 ANALYSIS PLAN

### 12.1 Study Endpoints

#### 12.1.1 Primary Endpoint

- **Safety and Tolerability:** AEs and cardiovascular responses including HR, BP, and ECG (including QTcF).

#### 12.1.2 Secondary Endpoints

- **Safety:** Clinical laboratory assessments
- **PK:** PK of cocaine and BE; PK of SXC-2023
- **Subjective Effects:** VAS and BSCS

### 12.2 Study Populations

#### 12.2.1 Safety Population

The safety population will include all participants who receive any administration of study drug.

### **12.2.2 Evaluable Population**

Any participant who completed all 5 infusion sessions will be considered evaluable for primary endpoints.

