#### 9.4 Blinding and Randomization (Day -1)

This is a double-blind, placebo-controlled, parallel group study. Eligibility criteria are re-reviewed on Day -1. A prospective participant who meets all of the study inclusion criteria and does not meet any of the exclusion criteria may be enrolled onto the study. After completing screening cocaine infusions (Session 1), participants will be randomized to receive either SXC-

2023 (10 participants) or matched placebo (10 participants). Participants will also be randomized to the order of the baseline and treatment cocaine and saline infusions.

The data-coordinating center will supply the Research Pharmacist with a randomization list. The Research Pharmacist will dispense the investigational agent for the participant to an investigator each day during treatment and infusion sessions.

Study participants who complete all 5 infusion sessions will be considered completed participants. This study requires 8 completed participants in each group. It is expected that, if 20 participants are randomized (10 for each group), there should be at least 8 completers in each group. Should there be 3 or more participants terminated in either group, replacement participant(s) will be assigned to that specific group.

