## 9.10 Individual Participant Stopping Criteria

Further participation of the participant in the study is stopped if any of the following criteria are met:

1. Acute chest pain
2. Systolic BP > 160 mmHg sustained for 5 minutes or more
3. Diastolic BP < 40 mmHg or > 100 mmHg sustained for 5 minutes or more
4. Heart rate < 40 bpm or > 160 bpm sustained for 5 minutes or more
5. QTcF  $\geq$  500 msec, or uncorrected QT interval > 600 msec
6. Clinically significant ECG changes in the opinion of an investigator

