### **6.4 Evaluable for Subjective Effects Analysis Population**

The Evaluable analysis set will include all participants who completed all 5 infusion sessions.

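### The analysis set for HR, BP and ECG is unsettled, and the only written rule selects completers through the same cardiovascular values

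*Protocol*

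**What the plan says.** Protocol 12.1.1 makes AEs and the cardiovascular responses (HR, BP, and ECG with QTcF) the primary endpoints. Protocol 12.2.2 then states: "Any participant who completed all 5 infusion sessions will be considered evaluable for primary endpoints". Protocol 12.4, which describes the AE, vital-sign and ECG analyses, names no population.

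The SAP is different. Section 6.4 is titled as the set for subjective effects and reads: "The Evaluable analysis set will include all participants who completed all 5 infusion sessions". Section 7.5.3 applies that set to VAS and BSCS. Section 7.4.1 puts AEs in the safety population. Section 7.4.2, which holds the HR and BP ANCOVA and the ECG summaries, names no set, and the opening of section 7 gives no default.

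Completion is tied to the cardiovascular measurements in two ways.
- Protocol 9.10: "Further participation of the participant in the study is stopped if any of the following criteria are met". The criteria include "Systolic BP > 160 mmHg sustained for 5 minutes or more", with similar sustained limits for diastolic pressure and heart rate, plus a QTcF limit.
- Protocol 9.7.1 and 9.7.2 require BP, HR and ECG to be within limits before cocaine is given on Days 8 and 9. BP or HR may be repeated once.

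Protocol 9.4 adds: "Should there be 3 or more participants terminated in either group, replacement participant(s) will be assigned to that specific group". Apart from partial dates, missing data are not imputed (Protocol 12.7, SAP 7).

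**The concern.** The trial asks whether SXC-2023 worsens the cardiovascular response to cocaine. If the HR and BP comparison is run in completers, membership of the set depends on the outcome measured after treatment. Should SXC-2023 raise the response, more of its high responders would reach a stopping limit in Session 4 or 5, or fail a pre-infusion check. They would leave the set, and the replacement rule could refill the arm with participants who tolerate the combination. The estimate would shrink toward no interaction, which is the unsafe direction for a safety question.

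If the completer rule is not meant to apply, the set for the primary cardiovascular test is simply undefined and could be chosen after the data are seen. With 8 completers planned per arm, one participant is 1/8 = 12.5% of an arm, so the choice matters.

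**Working it through.** **The plan's own figure.** The documents give no effect size, SD, power or dropout rate. Ten randomised per arm for 8 completers fits an unstated 20% non-completion: 8 / (1 − 0.20) = 10. At that rate the chance of at least 8 completers among 10 is 45(0.8⁸)(0.2²) + 10(0.8⁹)(0.2) + 0.8¹⁰ = 0.302 + 0.268 + 0.107 = 0.68 in one arm, and 0.68² = 0.46 in both. For both arms it is 0.87 at 10% non-completion and 0.15 at 30%. Replacement is therefore a realistic event.

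**Which stops can differ by arm.** Sessions 1 to 3 come before the first SXC-2023 or placebo dose on Day 3, so stops there cannot differ through a drug effect. Stops in Session 4 (Day 8, 20 mg) and Session 5 (Day 9, 40 mg) can.

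**What counts as completing Session 5.** The documents do not say. The second infusion follows the first by 60 minutes. With cocaine first, a stop prevents the saline infusion, so the session is arguably incomplete and the 40 mg values could fall out of a completer set. With saline first, both infusions have been given before a cocaine response can trigger a stop. Inclusion could thus depend on the randomised order. Both readings are shown below.

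**Illustration.** None of these inputs is in the documents except the 160 mmHg limit.
- Peak SBP for participant i in session s = μₛ + uᵢ + eᵢₛ + δ × (SXC-2023, Sessions 4 and 5 only).
- μ is 140 to 145 mmHg at 40 mg and 8 lower at 20 mg; SD(u) = 10, SD(e) = 8. This implies a total SD of √164 = 12.8 and a between-session correlation of 100/164 = 0.61.
- Any peak above 160 counts as a stop. This overstates stopping, because the rule needs 5 minutes sustained.
- The estimate is the treatment coefficient from an ANCOVA on the matching baseline session, among participants who passed Sessions 2 and 3.
- The DBP, HR and QTcF limits and the pre-infusion checks are not modelled.

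Results for δ = 10 mmHg (simulation error up to about 0.1):

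| Set | Day 8 (20 mg) | Day 9 (40 mg) |
|---|---|---|
| All who passed baseline, as if none stopped | about 10 | about 10 |
| Session 4 stops missing | 8.6 to 9.1 | 9.4 to 9.7 |
| Session 5 stops excluded too | see second set below | 6.9 to 7.8 |

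As losses from 10 mmHg, these are 9 to 14% on Day 8; on Day 9 they are 3 to 6% for Session 4 stops alone and 22 to 31% when Session 5 stops are also excluded. Completion is 90 to 94% on SXC-2023 against about 99% on placebo if only Session 4 stops count, and 68 to 79% against 92 to 96% if Session 5 stops count too.

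**Second set of assumptions.** Means 135/140 or 140/148 mmHg for 20/40 mg, SD 10 or 14, correlation 0.5 or 0.7, same treatment of the 160 limit:

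| True effect | Set | 20 mg | 40 mg |
|---|---|---|---|
| 10 | Session 4 stops excluded | 7.7 to 9.4 | 9.3 to 9.8 |
| 10 | Session 5 stops excluded too | 7.3 to 9.2 | 5.9 to 8.7 |
| 5 | Session 4 stops excluded | 4.1 to 4.9 | 4.7 to 5.0 |
| 5 | Session 5 stops excluded too | 3.9 to 4.8 | 3.2 to 4.6 |
| 0 | Either | about 0 | about 0 |

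**The case against.** The strongest reply is that the SAP has already narrowed the completer set. It retitles it for subjective effects, uses it only for VAS and BSCS, adds a full analysis set of all randomised participants, and analyses AEs in the safety population. Protocol 12.4.2 places vital signs and ECG under safety analyses. On this view a completers-only HR and BP analysis was never intended.

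Much of that stands, and it rules out three stronger readings.
- A reader might infer that all primary endpoints are analysed only in completers. AEs are not, by SAP 7.4.1. For HR, BP and ECG, a completer analysis is what Protocol 12.2.2 points to, not what the SAP prescribes.
- A reader might infer that the values behind a stop vanish from the report. They do not: clinically significant vital-sign and ECG findings are recorded as AEs (Protocol 11.6), AEs leading to discontinuation are listed (SAP 7.4.1), reasons for discontinuation are summarised by treatment (SAP 7.2.1), and data are listed (SAP 7). What is missing is a count by arm for each stopping criterion.
- A reader might take 6.9 to 7.8 mmHg as the expected Day 9 result. It arises only if participants stopped during Session 5 are classed as non-completers, which the documents do not settle. Nor are all large responses removed, since the BP and HR rules need a sustained excess.

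The reply does not close the gap. SAP 7.4.2 names no population. Elsewhere the SAP marks its departures from the protocol, as with the added and replaced AUC parameters in Table 7-1, but it never says that it replaces Protocol 12.2.2. That section remains the only text linking HR, BP and ECG to a set.

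**Conclusion.** The point holds for HR, BP and ECG as a conflict between documents and an unnamed analysis set, where the one written rule selects on the post-treatment outcome. If that rule were followed, a true pressor or heart-rate interaction would be understated; with no true effect there would be no bias.

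Only the direction is general. The sizes rest on assumed means, SDs and effects and on counting every peak above 160 mmHg as a stop. On those terms the loss is modest when only Day 8 stops matter, and larger at 40 mg only under the strict reading of Session 5 completion.

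Naming a better set does not settle everything. A participant stopped on Day 8, or refused the Day 9 infusion, has no 40 mg data in any population, so that comparison needs its own sensitivity analysis. VAS and BSCS are explicitly restricted to completers and share the selection; no size was computed for them.

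**What to change.** - **SAP 7.4.2:** for each session, analyse HR, BP and ECG in all randomised participants who took at least one SXC-2023 or placebo dose and received that session's cocaine infusion. Use all values up to any stop, and keep participants who were later replaced. Spelling the set out is safer than citing the safety population, because SAP 7.1 speaks of infusions of study drug as well as doses.
- **Protocol 12.2.2 and SAP 6.4:** reconcile them by removing the reference to primary endpoints from the protocol's definition.
- **By-arm table:** report the number meeting each stopping criterion and the number failing the Day 8 or Day 9 pre-infusion check.
- **Sensitivity analysis:** for participants with no 40 mg session because of a Day 8 stop or a failed check, add for example a rank analysis that gives them the worst rank.
- **SAP 7.5.3:** use the same per-session set for VAS and BSCS, with completers as a sensitivity analysis.

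The cost is SAP wording, one protocol sentence, one table and the added sensitivity analyses. No stopping rule, procedure or sample size changes.
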